## 10.4 Plan of Analysis

The principal analysis will aggregate patients from the two groups and will be conducted on a per-patient basis. We will calculate the concordance between the modalities across outcomes (combining cases and controls) and evaluate the results by calculating the kappa coefficient. Secondary endpoints will be calculated, both as aggregates of the three diseases and separately by disease. Sensitivities and other summaries will only be calculated if they involve a denominator of at least 10.

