## PROTOCOL SYNOPSIS

In the table below summarize the basic aspects of this research. This is to be used as a quick reference guide. Remove any section that is not relevant to the research.

TITLE	Combined $^{18}\text{F}$ NaF/ $^{18}\text{F}$ FDG PET/MRI for Detection of Skeletal Metastases
INDICATION	Breast cancer, lung cancer, prostate cancer
INVESTIGATIONAL PRODUCT OR PROCEDURE	$^{18}\text{F}$ NaF/ $^{18}\text{F}$ FDG PET/MRI
PRIMARY OBJECTIVE	Testing the hypothesis that the new simultaneous combined $^{18}\text{F}$ NaF/ $^{18}\text{F}$ FDG PET/MRI provide improved diagnostic accuracy over $^{99\text{m}}\text{Tc}$ MDP bone scanning
SECONDARY OBJECTIVE	
 
Evaluating the combined <math>^{18}\text{F}</math> NaF/<math>^{18}\text{F}</math> FDG PET/MRI as a reliable bone scanning modality
 
Evaluating the performance and reliability of the proposed WBMRI sequences
 

TREATMENT SUMMARY	No treatment
SAMPLE SIZE	170 participants: 10 from the pilot phase, 30 from PET/CT vs. WBMRI, 80 from first version of combined $^{18}\text{F}$ NaF/ $^{18}\text{F}$ FDG PET/MRI and 50 from second version of combined $^{18}\text{F}$ NaF/ $^{18}\text{F}$ FDG PET/MRI
STATISTICAL CONSIDERATIONS	
 
Per patient: concordance in cases, concordance in controls, sensitivity, specificity, positive predicted value, negative predictive value
 
Per lesion: distribution of lesions seen on each modality
 

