### 1.2. **Secondary Objectives**

- Evaluating the combined  $^{18}\text{F NaF}/^{18}\text{F FDG PET/MRI}$  as a reliable bone scanning modality
- Evaluating the performance and reliability of the proposed WBMRI sequences: IDEAL and eDWI
- Evaluating a fast MRI protocol (2:30 min/bed)

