### **3. PARTICIPANT SELECTION AND ENROLLMENT PROCEDURES**

#### **3.1 Inclusion Criteria**

- Patient is  $\geq 18$  years old at the time of the drug administration
- Patient provides written informed consent
- Patient is diagnosed with  $\geq$  stage 3 breast cancer or  $\geq$  stage 2 prostate cancer (and/or PSA  $>10$  micrograms/L), including patient with recurrent breast or prostate cancer
- Patient is scheduled to undergo a conventional bone scan
- Patient is capable of complying with study procedures
- Patient is able to remain still for duration of imaging procedure (about one hour)

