## 10. STATISTICAL CONSIDERATIONS

### 10.1 Populations

Patients with  $\geq$  stage 3 breast cancer or  $\geq$  stage 2 prostate cancer (and/or PSA >10 micrograms/L), including patients with recurrent breast or prostate cancer will be enrolled. The analysis subset will consist of patients with an interpretable  $^{99m}\text{Tc}$  MDP

bone scan,  $^{18}\text{F}$  NaF/ $^{18}\text{F}$  FDG PET/MRI evaluations, and a known clinical bone lesion evaluation at 12 months.

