### Secondary:

- Per patient: concordance in cases, concordance in controls, sensitivity, specificity, positive predicted value, negative predictive value
- Per lesion: distribution of lesions seen on each modality
- Proportion of diagnostic quality scans using the faster protocol compared to first cohort of 80 participants

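### As written, Sections 10.1 and 10.4 pool the 4 min/bed and 2:30 min/bed PET/MRI cohorts, so the fast protocol gets no concordance or accuracy estimate of its own

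*Combined protocol and SAP*

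**What the plan says.** - **Cohorts.** The synopsis divides 170 participants into four parts. Two of them had PET/MRI: "80 from first version of combined" PET/MRI, and 50 from a second version. Section 2.3 explains the change: 4 min/bed was too long for some elderly patients, so the MRI protocol is cut to 2:30 min/bed for the additional 50.
- **Objective.** Section 1.2 lists "Evaluating a fast MRI protocol (2:30 min/bed") as a secondary objective.
- **Analysis set.** Section 10.1: "The analysis subset will consist of patients with an interpretable" bone scan, PET/MRI evaluations and a known 12-month bone evaluation. Scan version is not mentioned.
- **Principal analysis.** Section 10.4: "The principal analysis will aggregate patients from the two groups and will be conducted on a per-patient basis". The groups are not identified there or elsewhere. The next sentence reads "We will calculate the concordance between the modalities across outcomes (combining cases and controls"), with kappa as the summary.
- **Planned splits.** Section 10.4: "Secondary endpoints will be calculated, both as aggregates of the three diseases and separately by disease". Summaries with a denominator below 10 are not calculated. The one result by scan version is in Section 10.3: "Proportion of diagnostic quality scans using the faster protocol compared to first cohort of 80 participants".

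**The concern.** The 50 new patients are scanned with a shortened acquisition, and evaluating that acquisition is an objective. The proportion of diagnostic-quality scans shows whether the faster images can be read. It does not show whether the readings agree with the bone scan or with the 12-month status. If the cohorts are pooled with no split, the reported concordance, kappa, sensitivity and specificity describe a mix of two acquisitions, weighted towards the one being dropped. A lower performance of the fast scan would be diluted in that average. A reader who wants to know how the 2:30 min/bed scan performed would find only the image-quality result.

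**Working it through.** **1. What the two groups can mean.** Three readings fit the text.

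| Reading | Source | Cohorts in the analysis |
|---|---|---|
| 80 and 50 PET/MRI patients | Synopsis | both, stated outright |
| Breast and prostate cancer | 3.1, "including patient with recurrent breast or prostate cancer" | set left to 10.1: both |
| Cases and controls | next sentence of 10.4 | set left to 10.1: both |

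All three lead to the same set of up to 80 + 50 = 130 patients. The label is unclear, but its consequence is not.

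**2. What is estimated by version.** Of the endpoints in 10.3, only the diagnostic-quality proportion is split by scan version. Concordance, kappa, sensitivity, specificity and the predictive values are planned in aggregate. The secondary ones are also planned by disease.

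**3. Weight of each version.** If all are evaluable: 80/130 = 61.5% at 4 min/bed and 50/130 = 38.5% at 2:30 min/bed. These weights apply to concordance. For sensitivity they hold only if the share of cases is the same in both cohorts.

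Illustration with assumed values: concordance of 85% in the 80 and 65% in the 50 pools to (68 + 32.5)/130 = 77.3%. A 20-point drop then appears as 85 − 77.3 = 7.7 points.

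**4. Precision of separate concordance estimates.** The documents give no concordance rate, so 80% is assumed. Wilson 95% intervals:

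- 2:30 min/bed, 40/50: 67.0% to 88.8% (half-width 10.9 points)
- 4 min/bed, 64/80: 70.0% to 87.3% (8.7 points)
- pooled, 104/130: 72.3% to 86.0%

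**5. Precision of a comparison between versions** (Wald half-widths, rates assumed):

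- Concordance, 80% in both: 1.96 × √[0.16 × (1/50 + 1/80)] = 14.1 points
- Concordance, 95% in both: 1.96 × √[0.0475 × (1/50 + 1/80)] = 7.7 points
- Specificity, 95% in both, 64 vs 40 controls: 1.96 × √[0.0475 × (1/64 + 1/40)] = 8.6 points
- Sensitivity, 90% vs 80%, 20% cases (16 vs 10): 1.96 × √(0.09/16 + 0.16/10) = 28.8 points
- Sensitivity, 90% vs 80%, 60% cases (48 vs 30): 1.96 × √(0.09/48 + 0.16/30) = 16.6 points

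Two-sided 5% power for that 10-point sensitivity difference is about 10% and 22% respectively.

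**6. The denominator-of-10 rule.** Sensitivity in the 50 needs 10/50 = 20% cases; in the 80 it needs 10/80 = 12.5%. Prevalence is not given. At an assumed 10, 20, 30 or 40%, the binomial chance of at least 10 cases among 50 is 2%, 56%, 96% or over 99%. Section 10.1 also requires 12-month status: if only 40 of the 50 have it (assumed), the required share rises to 10/40 = 25%. Concordance and kappa use all evaluable patients in the cohort, so the number of cases does not limit them.

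The Appendix sample sizes (84 and 233) concern paired sensitivities of the two modalities and do not bear on scan version.

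**The case against.** The strongest reply is that the objective in 1.2 already has its endpoint. It promises only an evaluation of the fast protocol. The stated reason for shortening is that patients find the scan too long, and the diagnostic-quality comparison with the first 80 fits that reason. Section 2.3 enrols the 50 to evaluate the combined PET/MRI further, which is consistent with pooling. This stands to the extent that the plan does not contradict itself, and it would be too strong to infer that the fast protocol gets no result at all. It does not supply agreement or accuracy for the fast scan, which image quality cannot replace.

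A reader might also infer that the plan leaves open whether only the 50 are analysed. Section 3.4 ties primary completion to the additional 50, and Section 5.2 describes only 2:30 min/bed. Those sections cover accrual and current acquisition, however. The section that defines the analysis set, 10.1, has no limit by version, so a 50-only analysis has no direct support.

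A third reply is that the split would be weak. For sensitivity that is right under the rates assumed above, and it is why the split should be descriptive. It would go too far to say that the intervals can neither show nor exclude a 10-point difference. That depends on unknown rates and on the method: with 95% concordance in both cohorts the Wald half-width is 7.7 points, while the upper Newcombe limit is about 10.3; at 98% that limit is about 8.6.

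**Conclusion.** The point holds as a modest, inexpensive improvement. Sections 10.1 and 10.4 together pool the two PET/MRI cohorts, and no planned analysis gives concordance, kappa, sensitivity or specificity for the 2:30 min/bed scan. With all patients evaluable, 62% of the pooled concordance comes from the 4 min/bed scan. A separate concordance estimate is feasible, at about ±11 points for an assumed 80% and n = 50. Separate sensitivity depends on prevalence and 12-month follow-up, which the documents do not quantify.

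Nothing in the documents shows that the two versions perform differently, so pooling should not be read as an error or as known bias. The dilution example only shows what could be masked.

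**What to change.** In Section 10.4, state that the principal analysis pools the 80 first-version and 50 second-version PET/MRI patients, and add:

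> Concordance, kappa, sensitivity and specificity will also be reported with 95% CIs separately for the 4 min/bed and 2:30 min/bed cohorts, with the case mix of each, subject to the denominator-of-10 rule; this comparison is descriptive because the cohorts are sequential.

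Case mix belongs in the table because kappa depends on the share of positive patients, which may differ between sequential cohorts. Leave out any statement about which difference the intervals can or cannot exclude, since that rests on rates not yet known.

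The cost is one defining phrase and one table from variables already planned, with no new patients, scans or tests. Section 2.3 already reports lesion findings for the 80 and describes the 50 as still to be enrolled, so the wording can be fixed before the 50 are analysed. The downside is wide intervals and possibly no sensitivity figure for the 50.

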## 10.5 Sample Size

A key parameter in determining the sample size for a study of the sensitivity and specificity of a new diagnostic modality relative to a standard modality is the degree of concordance of the modalities, or roughly speaking, the degree to which the modalities are correlated. The higher the concordance, the smaller the sample size required. For example, if current modalities for bone metastases detection ( $^{99\text{m}}\text{Tc}$  MDP bone scan) have a sensitivity of 80%, then the number of cases needed to demonstrate a 10% margin of superiority ranges from 83 to 284. Details are given in the Appendix

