## 10.7 Criteria for Future Studies

The accrual will continue until reaching the sample size required for statistical analysis, as described above, given the results from the previous 30 patients. The combined PET/MRI scanners are an ideal tool to evaluate this hypothesis.

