## 11. APPENDIX

The sample size follows Connett et al 1 . We replace the nomenclature of “Control” by “Old modality” and “Case” by “New Modality”. The numbers A, B,C D are the true probabilities summing to 1 as shown in the table:

	Old Modality		
New Modality	Positive	Negative	
Positive	A	B	Se.New
Negative	C	D	
	Se.Old		1

A convenient parametrization consists of

- ⤴ The proportion discordant  $K = B + C$
- ⤴ the sensitivity of the old modality  $Se.Old = A + C$ ,
- ⤴ the target improvement in sensitivity  $\Delta = (A + B) - (A + C) = B - C$

Connett et al adopt the parameterization:

- ⤴ Odds ratio  $\psi = B/C$
- ⤴ Proportion positive under old but negative under new  $P_{01} = C = (K + \Delta)/(K - \Delta)$

With this parametrization the sample size is given by

$$n = \frac{\left( z_{\alpha} \sqrt{\psi + 1} + z_{\beta} \sqrt{\psi + 1 - (\psi - 1)^2 P_{01}} \right)^2}{(\psi - 1)^2 P_{01}}$$

The Connett parameters can be derived thus:

$$P_{01} = (K - \Delta)/2 \text{ and } \psi = (K + \Delta)/(K - \Delta)$$

To illustrate, we set the sensitivity of the old modality to 0.8, Delta to 0.1, If we set the discordance close to its minimum value 0.11 we get the following table:

	Old Modality		
New Modality	Positive	Negative	
Positive	0.795	0.105	0.900
Negative	0.005	0.095	0.100
	0.800	0.200	1.000

With resulting OR=21, P01=0.005. With these parameters Connett's formula give N=84.

---

1 Connett, J. E., Smith, J. A., & McHugh, R. B. (1987). Sample size and power for pair-matched case-control studies. *Statistics in Medicine*, 6, 53-59.

If we set the discordance to 0.3 (maximum attainable with the other constraints) we get the table

	Old Modality		
New Modality	Positive	Negative	
Positive	0.700	0.200	0.900
Negative	0.100	0.000	0.100
	0.800	0.200	1.000

With resulting OR=2 P01=0.1, and the Connett formula gives a sample size of 233

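### Section 10.5 gives 83 to 284 cases, but the Appendix it relies on gives 84 and 233 for the same inputs, and its formula cannot produce both 83 and 284

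*Combined protocol and SAP*

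**What the plan says.** Section 10.5 takes a bone-scan sensitivity of 80% and states that "the number of cases needed to demonstrate a 10% margin of superiority ranges from 83 to 284", depending on how far the two modalities agree. It closes with "Details are given in the Appendix".

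The Appendix (section 11) starts from the same values: "To illustrate, we set the sensitivity of the old modality to 0.8, Delta to 0.1". It works two examples with a paired-proportions formula.

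- At discordance 0.11, close to the minimum: "With these parameters Connett's formula give N=84".
- At discordance 0.30, which it describes as the largest value possible under the other constraints: "the Connett formula gives a sample size of 233".

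The normal quantiles for alpha and power appear in the formula only as symbols. Neither section gives alpha, sidedness or power.

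Section 10.7 then says: "The accrual will continue until reaching the sample size required for statistical analysis, as described above". The sentence goes on to make this conditional on the results of the 30 patients studied earlier.

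**The concern.** The same sensitivity, the same margin and the same cited derivation lead to two different upper ends, 284 and 233. One explanation would be that section 10.5 used another alpha or power. Neither is stated, so that has to be tested before 284 can be called wrong.

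This range is the only quantitative support for sample size in the protocol, and section 10.7 points back to it. As printed, a reader cannot tell which upper figure applies or what error rates it assumes.

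**Working it through.** **Inputs.** Old sensitivity 0.80 and improvement Δ = 0.10 (section 10.5 and Appendix); discordance K = 0.11 and 0.30 (Appendix). Alpha and power are not given, so they are varied below.

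**Formula.** The Appendix uses ψ = (K+Δ)/(K−Δ) and P01 = (K−Δ)/2. Substituting these into its sample-size expression gives

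n = [z_α·√K + z_β·√(K − Δ²)]² / Δ²

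**Reproducing the Appendix.** At two-sided 0.05 (equivalently one-sided 0.025) and 80% power, z_α = 1.960 and z_β = 0.8416:

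- K = 0.11: [1.960·√0.11 + 0.8416·√0.10]² / 0.01 = 83.94, so 84.
- K = 0.30: [1.960·√0.30 + 0.8416·√0.29]² / 0.01 = 233.09, printed as 233.

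With quantiles rounded to 1.96 and 0.84 the results are 83.85 and 232.83, which round up to 84 and 233. One conventional setting therefore accounts for both Appendix figures.

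**Feasible discordance.** New sensitivity is 0.90, so cells C and D of the Appendix table sum to 0.10, and C = (K − 0.10)/2. C ≥ 0 requires K ≥ 0.10. D = 0.10 − C ≥ 0 requires K ≤ 0.30. This confirms the Appendix's maximum.

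**Can 284 arise at the Appendix's setting?** Solving n = 284 at two-sided 0.05 and 80% power gives K = 0.365. Then C = 0.132 and D = −0.032, a negative probability.

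**Can another alpha or power give both figures?**

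| Setting | n at K = 0.10 | n at K = 0.11 | n at K = 0.30 |
|---|---|---|---|
| Two-sided 0.05, 80% | 76.1 | 83.9 | 233.1 |
| Two-sided 0.05, 85% | 86.6 | 95.6 | 266.2 |
| Two-sided 0.05, 90% | 100.9 | 111.4 | 311.0 |
| Two-sided 0.05, 95% | 123.9 | 136.9 | 383.9 |
| One-sided 0.05, 80% | 59.7 | 65.9 | 183.4 |
| One-sided 0.05, 90% | 81.8 | 90.4 | 253.2 |
| One-sided 0.05, 95% | 102.7 | 113.6 | 319.2 |

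No row holds both. Settings that make 284 feasible lift the lower end away from 83:

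- At two-sided 0.05, n = 284 at K = 0.30 corresponds to 87.2% power. The lower end is then 93 (K = 0.10) or 102 (K = 0.11).
- At two-sided 0.05 and 90% power, 284 is reached at K = 0.274. The lower end is then 101 or 112.

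**General bound.** For any alpha below 0.5 and power of at least 50%, n(0.30)/n(0.10) lies between 0.30/0.10 = 3.00 and 0.29/0.09 = 3.22. Starting from the Appendix's K = 0.11, the limits are 0.30/0.11 = 2.73 and 0.29/0.10 = 2.90. The Appendix's own ratio, 233/84 = 2.77, fits. Section 10.5 needs 284/83 = 3.42, or 283/84 = 3.37 with the most generous rounding. Both exceed 3.22. A grid search over alpha and power found no pair giving both figures, even within a 3% tolerance.

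**Other methods at two-sided 0.05 and 80% power** (K = 0.11, then 0.30): continuity-corrected versions give 94 to 103 and 243 to 253; exact McNemar gives 86 and 249. Neither yields 83 and 284.

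**The case against.** The mismatch itself cannot be disputed; the arguments on the other side concern its cause and weight.

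- **A slip of one digit.** 233.09 rounded up is 234, and 284 differs from 234 by a single digit. A typing error, or a digit misread when the PDF was converted, would explain the figure without any wrong calculation. This is plausible but cannot be shown from the text. A typing error would still leave a wrong number in the protocol; a conversion error would not, and the sponsor can settle that by looking at the source file.
- **Little depends on it.** Both sections present the figures as examples. The synopsis plans 170 participants, of whom 80 + 50 = 130 have PET/MRI. Both 233 and 284 are counts of cases and exceed even the 170, so replacing one with the other alters no decision. This stands, and it limits the point to a consistency correction.
- **Section 10.7 is conditional.** It ties accrual to a sample size that takes account of the earlier 30 patients, not to the upper end of the range. That is fair. It still refers back to section 10.5, which is the only place above it where a requirement is given.
- **Another formula might fit.** A formula conditional on the discordant pairs can be forced to give 83 and 284 at a two-sided alpha of about 0.013 and about 73% power. The documents do not use that formula, the setting is not conventional, and it would not give the Appendix's 84 and 233.
- **233 or 234.** With unrounded quantiles, 233 has 79.98% power and 234 is the smallest integer that reaches 80%. The one-case difference is rounding and does not bear on 284.

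**Conclusion.** The concern holds. The upper end in section 10.5 exceeds the figure in its cited derivation by 284 − 233 = 51 cases (51/233 = 22%), and 83 to 284 is not a range that the Appendix formula can give within the feasible discordance of 0.10 to 0.30. That conclusion needs no assumed alpha or power beyond alpha below 0.5 and power of at least 50%.

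Two-sided 0.05 with 80% power is an inference: it reproduces both Appendix figures, but the documents do not state it. How 284 came about is unknown. The correction should be made because this is the protocol's only sample-size calculation; enrolment, endpoint and analysis are unaffected.

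**What to change.** In section 10.5, replace the range with 84 to 233 and name the discordance values it corresponds to (0.11 and 0.30). State the alpha, sidedness and power in section 10.5 or the Appendix. The sponsor should confirm these settings; two-sided 0.05 with 80% power reproduces the Appendix. The Appendix's 233 can stay as printed, provided the rounding convention is stated (234 if unrounded quantiles are used and the result is rounded up).

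One small tidy-up in the Appendix has no numerical effect. The line that introduces P01 equates it to (K+Δ)/(K−Δ), which is the odds ratio. It should read (K−Δ)/2, as the Appendix gives further down and as its printed values of 0.005 and 0.1 require.

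The cost is a text edit, with no change to enrolment, endpoint or analysis.

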identify extra-skeletal disease, represents a beneficial alternative to the single modalities performed separately.  $^{18}\text{F}$  NaF/ $^{18}\text{F}$  FDG PET/MRI is a promising approach for evaluation of skeletal and extra-skeletal lesions in a selected population of breast and prostate cancer patients. However, the current duration of exam (4 min/bed) is too long for some of the elderly patients. Therefore, we are now shortening the WBMRI protocol from 4 min/bed to 2:30 min/bed, reducing the total time from approximately 45 min/scan to 20-25 min/scan. We plan to enroll and have funding 50 additional subjects (25/year) to further evaluate the combined  $^{18}\text{F}$  NaF/ $^{18}\text{F}$  FDG PET/MRI as a reliable bone scanning modality.

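### Section 10.5 sizes the sensitivity comparison in patients with bone metastases, but accrual counts all patients: the 130 who can have PET/MRI reach the lower figure only if about 64% have metastases, and cannot reach the upper one.

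*Combined protocol and SAP*

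**What the plan says.** Section 10.5 takes a bone-scan sensitivity of 80% and states that "the number of cases needed to demonstrate a 10% margin of superiority ranges from 83 to 284", referring to the Appendix for details. The Appendix says "we set the sensitivity of the old modality to 0.8, Delta to 0.1" and works two scenarios. The first begins "If we set the discordance close to its minimum value 0.11 we get the following table" and ends with "formula give N=84". The second begins "If we set the discordance to 0.3 (maximum attainable with the other constraints" and arrives at 233.

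The Synopsis gives the sample size as "170 participants: 10 from the pilot phase, 30 from PET/CT vs. WBMRI, 80 from first version of combined" PET/MRI, followed by 50 from its second version. Section 2.3 describes the current extension as "50 additional subjects (25/year" and says it is funded. Section 10.1 limits the analysis subset to patients with an interpretable bone scan, an interpretable PET/MRI and "a known clinical bone lesion evaluation at 12 months". Section 10.4 pools two groups, which I read as the 80 and the 50. Section 10.7 continues accrual until the size described in the preceding sections is reached.

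**The concern.** The two sets of numbers are in different units. Sections 10.3 and 10.4 treat cases and controls as two parts of the enrolled population. The Appendix tables have sensitivities as their margins and sum to 1, so they describe only patients who truly have bone metastases. Recruitment, by contrast, takes eligible patients referred for a bone scan whatever their metastatic status. The plan gives no prevalence, expected number of cases or conversion from patients to cases.

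Someone who sets 130 or 170 beside a range of 83 to 284 will conclude that enrolment falls inside it. That comparison is not valid. If the sensitivity estimates then show no clear gain, they may be taken as evidence against a 10-point improvement that the number of cases could not have shown reliably.

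**Working it through.** **Inputs.** Old-modality sensitivity 0.80 and Δ = 0.10 (Appendix); discordance K = 0.11 and K = 0.30 (Appendix); 80 + 50 PET/MRI patients (Synopsis, Section 2.3). Alpha and power are not stated, so they are back-solved below. Prevalence is not stated, so it is assumed and shown as a range.

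**Step 1: reproduce the plan's figures.** The Appendix formula is n = [z_α√(ψ+1) + z_β√(ψ+1−(ψ−1)²P01)]² / [(ψ−1)²P01], with P01 = (K−Δ)/2 and ψ = (K+Δ)/(K−Δ). Take two-sided 5% and 80% power (z = 1.960 and 0.842).

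- K = 0.11: ψ = 21, P01 = 0.005, (ψ−1)²P01 = 2. n = (1.960√22 + 0.842√20)²/2 = 83.9. The Appendix has 84 and Section 10.5 has 83.
- K = 0.30: ψ = 2, P01 = 0.1, (ψ−1)²P01 = 0.1. n = (1.960√3 + 0.842√2.9)²/0.1 = 233.1. The Appendix has 233.

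The 284 in Section 10.5 does not reproduce. At these settings it would need K of about 0.365, above the Appendix's own maximum of 0.30. None of the alpha, power and continuity-correction settings tried gave both 83 and 284.

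**Step 2: the pool.** The 10 pilot patients had separate PET/CT scans and whole-body MRI, and the next 30 had combined PET/CT and whole-body MRI (Sections 2.3 and Synopsis). None of these 40 had the combined PET/MRI. The most that can enter the Section 10.1 subset is 170 − 40 = 130, before loss for uninterpretable scans or unknown 12-month status.

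**Step 3: prevalence needed.**

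| Cases required | Share of 130 |
|---|---|
| 83 (Section 10.5, lower) | 63.8% |
| 84 (Appendix, lower) | 64.6% |
| 233 (Appendix, upper) | 179% |
| 284 (Section 10.5, upper) | 218% |

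The 64% is a floor, because it takes nearly the smallest possible discordance and no losses. Counting all 170 would lower it to 83/170 = 48.8% and would still leave 233 and 284 out of reach.

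**Step 4: power at assumed prevalences.** The number of discordant cases is binomial(n, K). Given that number, those favouring the new modality are binomial with probability (K+Δ)/(2K). The test is exact McNemar, two-sided 5%.

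| Assumed prevalence | Cases of 130 | Power, K = 0.30 | Power, K = 0.11 |
|---|---|---|---|
| 30% | 39 | 13% | 19% |
| 40% | 52 | 19% | 40% |
| 50% | 65 | 24% | 59% |

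The exact test is used because discordant cases are few: at 39 cases and K = 0.11 only 39 × 0.11 = 4.3 are expected. Five discordant cases all in one direction give p = 2 × 0.5⁵ = 0.0625, so at least six are needed for significance. Inverting the Appendix formula gives 47% in that cell, which is too favourable.

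**The case against.** Section 10.5 introduces its figures as an example and the Appendix as an illustration. The primary endpoint in Section 10.3 is the proportion of patients in whom the modalities agree, evaluated by kappa over cases and controls together. Sensitivity is a secondary summary, calculated when its denominator is at least 10, and no test of it is specified. The upper scenario is a boundary: its table leaves no case missed by both modalities. The Synopsis itemises 170 by phase and never calls it the analysis set.

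Most of this stands, and it rules out several stronger readings that a reader might infer.

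- That the primary analysis is underpowered. The sensitivity calculation does not apply to overall concordance or kappa, so the documents do not support this.
- That the plan claims 170 analysable patients. It does not; Section 10.1 already excludes those without PET/MRI.
- That 233 or 284 cases are required. They are worst-case values, so failing to reach them does not by itself condemn the design.
- That prevalence is in fact below 64%. The documents give no prevalence.

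The objection does not remove the core. This is the only sizing argument in the plan, and Section 10.7 makes it operative by tying accrual to it. The primary objective is improved diagnostic accuracy, which agreement alone cannot show. Section 10.7 could be read as open-ended accrual, but it names no number of cases and sits beside a fixed, funded addition of 50.

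**Conclusion.** The point holds within those limits. The size in Section 10.5 is in cases, and the plan does not show that its enrolment delivers it. The lower figure needs at least 64% of 130 patients to have bone metastases, with every patient evaluable and discordance near its minimum. The worst-case upper figure is unattainable from 130 at any prevalence, whether it is taken as 233 or 284.

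These results rest on the document's own counts and on reading the two pooled groups as the 80 and the 50. If they were not pooled, neither cohort alone could supply 83 cases. The power figures rest further on assumed prevalence and back-solved alpha. The consequence falls on the accuracy objective and the secondary sensitivity endpoint. It is an omitted conversion from patients to cases, together with an unreconciled upper figure.

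**What to change.** In Section 10.5 and the Synopsis:

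- State that the PET/MRI analysis set is at most 130.
- Give expected cases and controls over a stated prevalence range. Use prevalence and discordance from the first 80 only where 12-month status is complete, since the documents do not show that it is. Say that those patients are also in the pooled analysis, so the planning figures are not independent of the results.
- Replace the range of 83 to 284 with the resulting 95% confidence-interval half-widths for the paired sensitivity and specificity differences.
- State that a 10-point sensitivity gain is not powered if fewer than 84 cases are expected, even at the most favourable discordance, and give the alpha and power behind that threshold.
- Reconcile 284 in Section 10.5 with 233 in the Appendix.

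In Section 10.7, reconcile accrual to a required size with the fixed addition of 50.

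This takes rewording and a short recalculation, with no extra patients and no change to endpoints. The cost is that the stated figures become less favourable.
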